Appendix 6 World Health Organization Toxicity Grading Scale (cont.)

Appendix: WHO TOXICITY GRADING SCALE FOR DETERMINING THE SEVERITY OF ADVERSE EVENTS

CHEMISTRIES (continued)				
Hyperglycemia (note if fasting)	116 - 160 mg/dL	161- 250 mg/dL	251 - 500 mg/dL	> 500 mg/dL or ketoacidosis or seizures
Hypocalcemia (corrected for albumin)	8.4 - 7.8 mg/dL	7.7 - 7.0 mg/dL	6.9 - 6.1 mg/dL	< 6.1 mg/dL or life threatening arrhythmia or tetany
Hypercalcemia (correct for albumin)	10.6 - 11.5 mg/dL	11.6 - 12.5 mg/dL	12.6 - 13.5 mg/dL	> 13.5 mg/dL life-threatening arrhythmia
Hypomagnesemia	1.4 - 1.2 mEq/L	1.1 - 0.9 mEq/L	0.8 - 0.6 mEq/L	< 0.6 mEq/L or life- threatening arrhythmia
Hypophosphatemia	2.0 - 2.4 mg/dL	1.5 -1.9 mg/dL or replacement Rx required	1.0 -1.4 mg/dL intensive Rx or hospitalization required	< 1.0 mg/dL or life- threatening arrhythmia
Hyperbilirubinemia	1.1 - 1.5 x ULN	1.6 - 2.5 x ULN	2.6 - 5 x ULN	> 5 x ULN
BUN	1.25 - 2.5 x ULN	2.6 - 5 x ULN	5.1 - 10 x ULN	> 10 x ULN
Creatinine	1.1 x 1.5 x ULN	1.6 - 3.0 x ULN	3.1 - 6 x ULN	> 6 x ULN or required dialysis
URINALYSIS				
Proteinuria	1+ or < 0.3% or <3g/L or 200 mg - 1 gm loss/day	2 -3 + or 0.3 - 1.0% or 3-10 g/L 1- 2 gm loss/day	4+ or > 1.0% or > 10 g/L 2-3.5 gm loss/day	nephrotic syndrome or > 3.5 gm loss/day
Hematuria	microscopic only	gross, no clots	gross+ clots	obstructive or required transfusion
CARDIAC DYSFUNCTION				
Cardiac Rhythm		asymptomatic, transient signs, no Rx required	recurrent/persistent; No Rx required	requires treatment
Hypertension	transient inc. > 20 mm; no Rx	recurrent, chronic, > 20 mm, Rx required	requires acute Rx; No hospitalization	requires hospitalization
Hypotension	transient orthostatic hypotension, No Rx	symptoms correctable with oral fluids Rx	requires IV fluids; no hospitalization required	requires hospitalization
Pericarditis	minimal effusion	mild/moderate asymptomatic effusion, no Rx	symptomatic effusion; pain; EKG changes	tamponade; pericardiocentesis or surgery required
Hemorrhage, Blood Loss	microscopic/occult	mild, no transfusion	gross blood loss; 1-2 units transfused	massive blood loss; > 3 units transfused

Appendix 6 World Health Organization Toxicity Grading Scale (cont.)

**Appendix: WHO TOXICITY GRADING SCALE FOR DETERMINING
THE SEVERITY OF ADVERSE EVENTS**

RESPIRATORY				
Cough	transient- no Rx	treatment associated cough local Rx	uncontrolled	
Bronchospasm, Acute	transient; no Rx < 80% - 70% FEV ₁ (or peak flow)	requires Rx normalizes with bronchodilator; FEV ₁ 50% - 70% (or peak Flow)	no normalization with bronchodilator; FEV ₁ 25% - 50% (or peak flow retractions)	cyanosis: FEV ₁ < 25% (or peak flow) or intubated
GASTROINTESTINAL				
Stomatitis	mild discomfort; no limits on activity	some limits on eating/drinking	eating/talking very limited	requires IV fluids
Nausea	mild discomfort; maintains reasonable intake	moderate discomfort; intake decreased significantly; some activity limited	severe discomfort; no significant intake; activities limited	minimal fluid intake
Vomiting	transient emesis	occasional/moderate vomiting	orthostatic hypotension or IV fluids required	hypotensive shock or hospitalization required for IV fluid therapy
Constipation	mild	moderate	severe	distensions w/vomiting
Diarrhea	transient 3-4 loose stools/day	5-7 loose stools/day	orthostatic hypotension or > 7 loose stools/day or required IV fluids	hypotensive shock or hospitalization for IV fluid therapy required
NEURO & NEUROMUSCULAR				
Neuro-Cerebellar	slight incoordination dysdiadochokinesis	intention tremor, dysmetria, slurred speech; nystagmus	locomotor ataxia	incapacitated
Mood	mild anxiety or depression	moderate anxiety or depression and therapy required	severe anxiety or depression or mania; needs assistance	acute psychosis; incapacitated, requires hospitalization
Neuro Control (ADL = activities of daily living)	mild difficulty concentrating; no Rx; mild confusion/agitation; ADL unaffected	moderate confusion/agitation some limitation of ADL; minimal Rx	severe confusion/agitation needs assistance for ADL; therapy required	toxic psychosis; hospitalization
Muscle Strength	subjective weakness no objective symptoms/ signs	mild objective signs/symptoms no decrease in function	objective weakness function limited	paralysis

Appendix 6 World Health Organization Toxicity Grading Scale (cont.)

**Appendix: WHO TOXICITY GRADING SCALE FOR DETERMINING
THE SEVERITY OF ADVERSE EVENTS**

OTHER PARAMETERS				
Fever: oral, > 12 hours	37.7 - 38.5 C or 100.0 - 101.5 F	38.6 - 39.5 C or 101.6 - 102.9 F	39.6 - 40.5 C or 103 - 105 F	> 40 C or > 105 F
Headache	mild, no Rx therapy	transient, moderate; Rx required	severe; responds to initial narcotic therapy	intractable; required repeated narcotic therapy
Fatigue	no decrease in ADL	normal activity decreased 25- 50%	normal activity decreased > 50% can't work	unable to care for self
Allergic Reaction	pruritus without rash	localized urticaria	generalized urticaria; angioedema	anaphylaxis
Local Reaction	tenderness or erythema	induration < 10 cm or phlebitis or inflammation	induration > 10 cm or ulceration	necrosis
Mucocutaneous	erythema; pruritus	diffuse, maculo papular rash, dry desquamation	vesiculation, moist desquamation, or ulceration	exfoliative dermatitis, mucous membrane involvement or erythema, multiforme or suspected Stevens- Johnson or necrosis requiring surgery

This Phase II, multicenter, randomized, double-blind, placebo-controlled, parallel-group study will evaluate the efficacy, safety and tolerability, pharmacokinetics, and pharmacodynamics of Semorinemab (MTAU9937A) in patients with prodromal-to-mild Alzheimer's Disease (AD).

MTAU9937A is a pan-tau IgG4 monoclonal antibody that has the potential to treat tauopathies (including AD and primary tauopathies). MTAU9937A is designed to bind and intercept all extracellular tau isoforms, in order to stop or slow cell-to-cell spread and propagation of tau toxicity and pathology throughout cortical and sub-cortical networks. In addition to this Phase II clinical study (GN39763), the safety and efficacy of MTAU9937A in AD is also being evaluated in the ongoing LAURIET Phase II study in moderate AD (GN40040).

Fluorine-18 Genentech tau probe 1 (^{18}F]GTP1 or RO6880276) has been developed as a positron emitting radioligand for in vivo imaging of tau protein aggregates. ^{18}F]GTP1 has been previously evaluated in a first-in-human study (e0040) involving 3 patients with AD, 3 patients with progressive supranuclear palsy, and 2 HVs. The study demonstrated substantial retention of the radioligand in brain regions expected to contain tau pathology in patients with AD. ^{18}F]GTP1 has also been studied in two additional Phase I studies: a test re-test study (e0048) with 5 patients with AD and 5 elderly HVs, and a radiation dosimetry study (e0049) with 6 HVs. In addition, ^{18}F]GTP1 is currently being evaluated in a Phase I longitudinal natural history study (Study GN30009; clinicaltrials.gov identifier NCT02640092).

^{18}F]GTP1 is also being evaluated in a longitudinal PET-imaging substudy of two Phase III trials of the anti-A β antibody gantenerumab (Studies WN29922 and WN39658; clinicaltrials.gov identifiers NCT03444870 and NCT03443973, respectively) as well as a PET-imaging substudy of a Phase II trial of the anti-A β antibody crenezumab (study GN28352; clinicaltrials.gov identifier NCT01998841). It also has been evaluated in a longitudinal PET-imaging substudy of two discontinued Phase II trials of the anti-A β antibody crenezumab (Studies BN29552 and BN29553; clinicaltrials.gov identifiers NCT02670083 and NCT03114657, respectively).

2. **STUDY DESIGN**

The study consists of a screening period, a double-blind treatment period, an optional OLE period, and a safety follow-up period (see protocol for details). An extended baseline visit (up to 15 days) is included in the double-blind treatment period, following randomization and prior to the initiation of study drug. Study drug (MTAU9937A or placebo) will be administered intravenously in the double-blind treatment period, and MTAU9937A will be administered intravenously in the optional OLE period. Study drug administration will occur every 2 weeks (Q2W) for the first three doses of the double-blind treatment period and every 4 weeks (Q4W) thereafter in the double-blind treatment period. MTAU9937A will be administered Q4W in the OLE period. Study treatment is defined as study drug plus the PET radioligand used during PET imaging procedures (^{18}F]GTP1 for tau PET imaging and the amyloid radioligand for amyloid PET imaging).

This study has enrolled 457 patients at 97 sites in North America, Europe, and the Asia-Pacific region. Patients were randomly assigned to one of three active, IV dose arms (1500 mg, 4500 mg, or 8100 mg MTAU9937A) or to an IV placebo dose arm in a 2:3:2:3 (1500 mg:4500 mg:8100 mg:placebo) ratio. All patients participating in the OLE will receive

MTAU9937A 4500 mg IV. To maintain balance in dementia status and APOE status between treatment arms, randomization will be stratified by dementia status (pAD vs. mAD) and APOE status (ApoE4+ vs. ApoE4-).

2.1 OUTCOME MEASURES

2.1.1 Primary Efficacy Endpoint

Change in CDR-SB score from baseline to Week 73 (refer to Section 4.4 for detailed derivation)

2.1.2 Secondary Efficacy Endpoints

The secondary efficacy endpoints of this study are as follows:

- Change in ADAS-Cog13 score from baseline to Week 73
- Change in ADCS-ADL score from baseline to Week 73
- Change in RBANS total score from baseline to Week 73
- Change in Amsterdam iADL score from baseline to Week 73

2.1.3 Safety Endpoints

The safety endpoints are as follows:

- Nature, frequency, severity, and timing of adverse events and serious adverse events. Severity of adverse events will be determined through the use of the WHO toxicity grading scale.
- Changes from baseline in vital signs, physical findings, neurologic findings, ECG, and clinical laboratory results during and following MTAU9937A administration
- Changes from baseline in suicidal ideation and behavior during and following MTAU9937A administration as assessed by the C-SSRS
- Nature, frequency, severity, and timing of neuroimaging abnormalities

2.1.4 Exploratory Biomarker Endpoints

The key exploratory biomarker endpoints are as follows:

- Change in [¹⁸F]GTP1 tau PET imaging from baseline through Week 73
- Change in levels of CSF tau species from baseline through Week 73

2.2 DETERMINATION OF SAMPLE SIZE

This study enrolled 457 patients randomized to one of three active IV dose arms or to an IV placebo dose arm in a 2:3:2:3 ratio. This sample size provides reasonable precision for estimating a clinically significant treatment effect on CDR-SB scores when MTAU9937A is compared with placebo. Assuming an observed 0.6-point difference in mean CDR-SB decline between the 4500 mg MTAU9937A arm and placebo at Week 73 (a 40% relative reduction in decline versus placebo), a standard deviation across patients of 2, and a 25% dropout rate, a 90% confidence interval on the population treatment effect point estimate for the CDR-SB is approximately 0.14–1.06.

The primary analysis detailed in Section 4.4 proposes the first hypothesis test for CDR-SB be a comparison between a single pooled 4500 mg and 8100 mg dose arm versus placebo (pre-dropout n = 228 and 137, respectively). Assuming a true 0.6-point difference in mean CDR-SB decline between the pooled MTAU9937A arm and placebo at Week 73 (a 40% relative reduction in decline versus placebo), a standard deviation across patients of 2, and a 25% dropout rate, this hypothesis test is expected to have 68% power at the alpha = 0.05 level.

2.3 ANALYSIS TIMING

The analysis will be conducted once all patients have either completed the Week 73 assessment or discontinued the study. At the time of analysis, treatment assignments will be unblinded to Sponsor personnel. At this time, all patients enrolled in the study will have either discontinued or transitioned into the open-label extension period of the study. All non-Sponsor personnel who are involved in the conduct of the study (e.g. patients, site monitors, and investigators) will remain blinded to treatment assignments until all patients complete the blinded safety follow-up period or transition into the OLE.

3. STUDY CONDUCT

3.1 RANDOMIZATION ISSUES

Patients will be randomly assigned to one of three active, IV dose arms (1500, 4500, or 8100 mg MTAU9937A) or to an IV placebo dose arm in a 2:3:2:3 (1500mg:4500 mg: 8100 mg:placebo) ratio. Randomization of patients will be managed by a central interactive voice or Web-based response system (IxRS) vendor using stratified permuted block randomization. The randomization will be stratified by dementia status (pAD vs. mAD) and APOE status (ApoE4+ vs. ApoE4-). The iDCC vendor periodically checks the IxRS to ensure that randomization is being performed correctly and that the correct kits are being assigned.

3.2 INDEPENDENT REVIEW FACILITY

Clinicians/raters (but not caregivers or patients) will use an electronic device to capture clinical outcome assessment (COA) data from all patients and/or caregivers enrolled in this study. This includes the primary and all secondary endpoints. COA data from the electronic device will be transmitted to a centralized database maintained by the electronic device vendor.

The COA scales and assessments for this study will be provided unless otherwise specified. Whenever possible, there should be consistency in the rater and caregiver who complete the scales for each patient throughout the duration of the study. Potential raters should be designated at each site and will receive training and be approved by the rating-scale vendor prior to being allowed to administer any cognitive assessments/ rating scales in the study. Administration of cognitive assessments/rating scales (i.e., the COAs) will be done in accordance with instructions provided in the GN39763 COA Manual and the training/documentation provided by the rating-scale vendor.

In addition, given that the primary outcome measure in this study involves subjective judgment, the adequacy of patient interviews and ratings will be monitored by an endpoint reliability program administered by the rating-scale vendor; this is considered to be an essential part of good research methodology. Prior studies have clearly demonstrated that the failure to

adequately monitor such ratings can substantially increase the risks of failed trials ([Becker and Greig 2008](#); [Kobak 2010](#)).

Please see the GN39763 COA Manual for instructions on COA administration order, specification of list versions to use at each visit, rater roles, restrictions on raters, and additional details on COA administration and the endpoint reliability program.

3.3 DATA MONITORING

The incidence and nature of adverse events, serious adverse events, and adverse events of special interest; responses on the C-SSRS; and abnormalities in vital signs, standard safety blood tests, ECG, and MRI will be assessed on a regular basis, approximately every 3-4 months, by an unblinded iDMC. The unblinded iDMC may also receive select summary statistics of COA endpoints.

At each safety review meeting, the iDMC will meet in a closed session to recommend whether the study should continue without modification, continue with minor modification, continue with substantial modification, suspend enrollment or treatment, or be terminated. There are currently no planned interim analyses to stop the trial early for either futility or clear signs of efficacy. Details of the iDMC are provided in the iDMC Charter.

The Sponsor also monitors all safety data continuously on a blinded basis.

4. STATISTICAL METHODS

The primary statistical analyses will be performed using SAS software (Version 9.2 or higher). R software (Version 3.3.2 or higher) may be used for creating figures, for QC purposes, and for sensitivity and subgroup analyses.

4.1 ANALYSIS POPULATIONS

Two analysis populations are defined for this study: the modified intend-to-treat (mITT) population and the safety-evaluable population.

4.1.1 Modified Intent-to-Treat Population

Efficacy analyses for each endpoint will be performed on the modified intent-to-treat population (mITT). For the primary and each secondary endpoint, the mITT population will include all randomized patients that have both a baseline measurement and at least one post-baseline measurement for the primary endpoint. The treatment groups will be based on the treatment assigned at randomization.

4.1.2 Safety-Evaluable Population

The safety-evaluable population will include all patients who were randomly allocated and received at least one dose of study drug (MTAU9937A or placebo) during the double-blind treatment period with treatment groups defined according to actual treatment received.

4.2 ANALYSIS OF STUDY CONDUCT

The number of patients who enroll, discontinue (early discontinuation of treatment or early termination from the study), complete the study (through Week 73), and continue into the OLE will be tabulated by treatment group. Reasons for early discontinuation of treatment or early termination from the study will be listed and summarized by treatment group. Any eligibility criteria exceptions and other major protocol deviations will also be summarized by treatment group.

4.3 ANALYSIS OF TREATMENT GROUP COMPARABILITY

Demographic and baseline characteristics such as age, sex, race, ApoE4 status, and baseline MMSE score will be summarized with means, standard deviations, medians, and ranges for continuous variables and with frequencies and proportions for categorical variables, as appropriate. Summaries will be presented by treatment arm and overall.

4.4 EFFICACY ANALYSIS

All efficacy analyses will be based on the modified intent-to-treat populations defined in Section 4.1.2. The primary and secondary endpoints will be analyzed as change scores, calculated as follows:

Outcome measure change score = (post-baseline value – baseline value)

In the above determination of change score for CDR-SB and RBANS, the baseline value will be defined as the average of all non-missing values before the first dose of study drug, which should be an average of the screening and baseline values. For all other cognitive and biomarker endpoints, baseline value will be defined as latest observed value before the first dose of study drug.

For the primary and secondary endpoints, mean changes from baseline will be compared across treatment arms using mixed-models for repeated measures (MMRM). Each model will have an intercept term, a term for baseline value of the endpoint, a term for APOE4 strata (carrier vs. non-carrier), a term for dementia status strata (pAD vs. mAD), an interaction term of the two stratification factors, categorical visit terms, a term for treatment group, a term for baseline age, and terms for treatment-by-visit interactions. This will be implemented using SAS proc mixed syntax similar to the excerpt below:

```
proc mixed data=data;  
class PATNUM VISIT TRT APOE4 DEMSTATUS;  
model var = BASE BAGE APOE4 DEMSTATUS APOE4*DEMSTATUS VISIT TRT TRT*VISIT  
/solution noint ddfm=kr;  
repeated VISIT / subject=PATNUM type=UN;  
lsmeans VISIT*TRT / pdiff cl alpha=0.05;  
estimate 'MTAU9937A vs Placebo Wk 73' TRT -1 1/cl;
```

An unstructured variance-covariance matrix for within-subject errors will be assumed. If the unstructured covariance structure matrix results in a lack of convergence, the heterogeneous Toeplitz covariance structure followed by the heterogeneous first-order autoregressive

covariance structure will be used. In these cases, the sandwich estimator will be used to get the variance of the treatment effect estimator.

If model assumptions are violated (e.g. large deviations from normality of residuals), alternative modeling strategies including data transformations, permutation-based approaches, and/or robust mixed effects modeling methodology (Koller, Journal of Statistical Software 2016) will be used as appropriate for additional sensitivity analyses.

Comparisons of Interest

Comparisons of efficacy will be performed between each MTAU9937A treatment arm and the placebo group by first pooling data from the middle and high doses for the first statistical test of the primary endpoint and then subsequently testing each treatment arm individually. Thus, there will be four comparisons across the doses:

MTAU9937A dose groups for hierarchical testing:

- **Group 1:** MTAU9937A 4500 mg + MTAU9937A 8100 mg vs placebo
- **Group 2:** MTAU9937A 4500 mg vs placebo
- **Group 3:** MTAU9937A 8100 mg vs placebo
- **Group 4:** MTAU9937A 1500 mg vs placebo

One model pooling middle and high doses will be used to test the Group 1 hypothesis. A second model including all 3 active arms separately will be used for Groups 2-4.

Type I Error Management

Type I error for the primary endpoint will be controlled using a fixed sequence testing procedure at the two-sided 5% significance level. The testing procedure will proceed with comparisons following the order across the four dose groups detailed above. After the first hypothesis test, each subsequent hypothesis will only be formally tested if the preceding one is significant at the 5% level.

For each dose group that has a significant result for the hypothesis test for the primary endpoint, a separate fixed sequence testing procedure will be ungated for that dose group's secondary endpoints that will similarly proceed at the 5% level. The overall testing procedure is detailed visually in the table below.

		MTAU9937A Dose group			
Endpoint		Group 1	Group 2	Group 3	Group 4
Primary	Change in CDR-SB score from baseline to Week 73				
Secondary	1. Change in ADAS-Cog13 score from baseline to Week 73	↓	↓	↓	↓
	2. Change in ADCS-ADL score from baseline to Week 73	↓	↓	↓	↓
	3. Change in RBANS total score from baseline to Week 73	↓	↓	↓	↓
	4. Change in Amsterdam iADL score from baseline to Week 73	↓	↓	↓	↓

No control for type I error will be applied for the exploratory endpoints, including sensitivity, subgroup, and biomarker analyses. Efficacy analyses will not involve formal comparisons between the MTAU9937A treatment arms.

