3.3.2 Rationale for Patient Population

The patient selection approach is consistent with the NIA-AA research diagnostic criteria and guidelines for AD as well as with the Qualification Opinion from the European Medicines Agency's Committee for Medicinal Products for Human Use on the use of CSF biomarkers and/or PET-amyloid imaging for enrichment of trials in mild to moderate AD dementia (2012), and U.S. Food and Drug Administration (FDA) draft guidance for early AD (2013). Although the FDA guidance refers to the early stage of AD in which individuals present with MCI, biomarkers of amyloid pathology are expected to add value to patient selection in mAD studies (see Section 3.3.3).

Patients in this study are also required to meet standard research criteria for mAD (according to the NIA-AA research criteria and guidelines for AD; [Appendix 3](#)) or pAD (according to the NIA-AA research criteria and guidelines for MCI; [Appendix 4](#)). Patients with pAD will present with documented objective evidence of deficit in at least one cognitive domain. Patients with mAD will present with documented deficits in at least two cognitive domains and in functional decline. Overall, the population will have an MMSE of ≥ 20 points and a CDR-GS of between 0.5 and 1.0. The MMSE score provides evidence of mild disease severity, and the CDR-GS score indicates that the patients have noticeable amnesic (pAD) or cognitive and functional deficits (mAD).

To ensure that the patients selected are likely to decline over the length of the study, two approaches have been included. The first is that all patients have to demonstrate amnesic deficits as measured by the Delayed Recall index of the RBANS (see Section 4.5.7.3). The Delayed Recall index of ≤ 85 has been selected, corresponding to one standard deviation below population-based normative data.

The second approach to ensure decline is to verify that there is evidence of prior decline through observations made by clinician or caregiver and recorded on the DVF. Enrollment into this study is subject to adjudication of diagnosis by the Sponsor or

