4.4.2 Secondary Efficacy Endpoints

Secondary endpoints listed below will similarly be analyzed and reported using the methods described in Section 4.4.1 using the MMRM model described in Section 4.4. The secondary endpoints for this study are listed below:

- Change in ADAS-Cog13 score from baseline to Week 73
- Change in ADCS-ADL score from baseline to Week 73
- Change in RBANS total score from baseline to Week 73
- Change in Amsterdam iADL score from baseline to Week 73

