4.4.3 Sensitivity Analyses

Mixed-models for repeated measures (MMRM) methods have been selected for the primary and secondary analyses due to their ability to accommodate the potential effects of missing data. An advantage of such models is that they rely on the assumption that the missing data mechanism is missing-at-random (MAR), rather than the more restrictive assumption that it is missing-completely-at-random (MCAR).

To evaluate the robustness of MMRM analyses to potential effects of missing data and validity of the MAR assumption, sensitivity analyses will be performed in the mITT population for the co-primary and secondary endpoints. At each time point (Week 25, Week 49, and Week 73), an ordinary least squares model for the change scores at that timepoint will be fit to estimate the treatment effect. These models will have terms for the baseline value of the endpoint, APOE4 strata, dementia status strata, the interaction between APOE4 strata and dementia status strata, baseline age, and treatment effect. These models will be fit using the following imputations for missing data:

- No imputation (a completer analysis)
- Using linear extrapolation imputation based on the values at baseline and the last week with a non-missing value
- Using last-observation-carried-forward
- Tipping point analysis

Intercurrent events may also influence the primary endpoint even if they do not directly result in missing data. Additional sensitivity analyses will be conducted using the above methods, but treating data collected after a given intercurrent event as missing. Proposed intercurrent events include missed study drug administration and initiation or modification of AD symptomatic concomitant medications. A separate section detailing intercurrent events and protocol deviations due to COVID-19 is included below. We propose to apply the same set of sensitivity analyses listed above when considering this additional set of intercurrent events.

Additional analyses looking at treatment effect estimates in subpopulations of patients receiving at least a minimum number of doses will also be conducted to assess if any observed treatment effect could have been potentially diluted by patients who did not fully adhere to the study drug administration schedule.

COVID-19 Sensitivity Analyses

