4.4.4 Subgroup Analyses

Exploratory subgroup analyses of the primary efficacy endpoint will be performed to evaluate the consistency of the primary analysis results across pre-specified subgroups defined by demographic and baseline characteristics. The following subgroups will be analyzed with respect to the primary efficacy endpoint:

- Age (≤ 65 years, > 65 years)
- Sex (male, female)
- Dementia status (prodromal, mild)
- APOE4 status (positive, negative)
- Geographic region (North America, EU, rest-of-world)

Biomarker subgroup analyses are specified in Section 4.4.5.

For above subgroup analyses, a MMRM model as specified for the primary analysis in Section 4.4 will be used for each subgroup analyses based on the available data subset for the patient subgroup of interest with the exception of the dementia status and APOE4 status subgroup analyses (bullets 3 and 4) which will not contain the respective indicator variables since they are being used to define the subgroup.

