4.6 MISSING DATA

A careful examination of reasons for study discontinuation will be conducted to assess the nature of incomplete data. In addition, frequencies and percentages of missing data at Week 73 will be compared between the two treatment arms. Missing data will not be imputed for the

primary analysis, but will instead be handled via the missing-at-random (MAR) assumption from the MMRM model as described in Section 4.4. Analyses to explore the sensitivity of results to missing data assumptions will be conducted as described in section 4.4.3. The issue of missing data for secondary and exploratory endpoints will be handled similarly with a MMRM model.

Patients who discontinue the study will be included in the analysis up to the date of study discontinuation.

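### The primary MMRM gives baseline CDR-SB and dementia status one coefficient for all visits; crossing baseline with visit is a cheap improvement, not the correction of an error

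*SAP*

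**What the plan says.** SAP Section 4.4 describes the model in words: "Each model will have an intercept term, a term for baseline value of the endpoint, a term for APOE4 strata (carrier vs. non-carrier" and so on through dementia status, the interaction of the two strata, visit, treatment and age. The only interaction with visit is treatment. The SAS excerpt agrees: "model var = BASE BAGE APOE4 DEMSTATUS APOE4*DEMSTATUS VISIT TRT TRT*VISIT". The residual covariance is unstructured.

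Three other sections bear on this model:

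- **Section 4.4.2:** the secondary endpoints "will similarly be analyzed and reported using the methods described in Section 4.4.1 using the MMRM model described in Section 4.4".
- **Section 4.6:** nothing is imputed for the "primary analysis, but will instead be handled via the missing-at-random (MAR) assumption from the MMRM model".
- **Section 2.2:** for the first comparison (pooled 4500 mg and 8100 mg against placebo), "this hypothesis test is expected to have 68% power at the alpha = 0.05 level".

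Two sets of supporting analyses let the covariate effects vary more freely. The models in Section 4.4.3 are fitted separately at Weeks 25, 49 and 73: "These models will have terms for the baseline value of the endpoint, APOE4 strata, dementia status strata", with their interaction, age and treatment. The dementia-status and APOE4 subgroup models in Section 4.4.4 drop the stratum term, "which will not contain the respective indicator variables since they are being used to define the subgroup".

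**The concern.** The outcome is change from baseline. A covariate that predicts the rate of decline has little time to act by Week 25 and most time by Week 73. A single coefficient must compromise between visits and can be too flat at the only visit that is tested.

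Two things could follow. First, some baseline-related variation stays in the Week 73 residual, so the contrast is slightly less precise. Second, the MMRM carries patients who drop out forward through this same mean model. If the Week 73 slope is too flat, the expected decline of sicker dropouts is understated. If one arm loses more of them, that arm looks better than it should, even though data are missing at random given baseline and earlier visits.

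The first test opens the whole testing sequence, and this model is the primary analysis's only handling of missing data, so a nearly free improvement is worth having.

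**Working it through.** **1. The plan's own figures.** SAP Section 2.2 gives 228 and 137 patients, SD 2, 25% dropout and a difference of 0.6. Completers are 228 × 0.75 = 171 and 137 × 0.75 = 102.75.

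- SE = 2 × √(1/171 + 1/102.75) = 0.250. Power = Φ(0.6/0.2496 − 1.96) = Φ(0.443) = 67.1%, against 68% stated.
- 90% interval for 4500 mg against placebo: SE = 2 × √(2/102.75) = 0.279, and 0.6 ± 1.645 × 0.279 = 0.14 to 1.06, as stated.

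Both reproduce. Neither uses a covariate, so neither depends on the point at issue.

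**2. Inputs that the documents do not give.** The baseline slope by visit, baseline SD, between-visit correlations and dropout by arm are all assumed. Main set: residual SD 1.1 and 1.5 at Weeks 25 and 49; total SD 2 at Week 73; residual correlations 0.6 (Weeks 25-49), 0.5 (25-73) and 0.7 (49-73); baseline explaining a share p of Week 73 variance.

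**3. Complete-data formula.** Let β be the true Week 73 coefficient and b the shared one. Sharing multiplies the Week 73 variance by 1 + (1 − b/β)² × p/(1 − p). The shared b is a weighted average of the visit-specific coefficients, with weights proportional to the column sums of the inverse residual covariance. For p = 10% the weights are 0.852, 0.152 and −0.004: Week 25 dominates because its residual SD is smallest.

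- Proportional growth (1/3, 2/3, 1): b/β = 0.852/3 + 0.152 × 2/3 − 0.004 = 0.381. Ratio = 1 + 0.619² × 0.10/0.90 = 1.043.
- Milder growth (0.6, 0.8, 1): b/β = 0.629. Ratio = 1 + 0.371²/9 = 1.015.
- Constant effect: b/β = 1. Ratio = 1.

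**4. Simulation with dropout** (228 against 137 patients, 25% dropout in each arm related to baseline, 20,000 trials, maximum likelihood), shared model against `BASE*VISIT`:

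| Growth | p | Formula | Simulated variance ratio |
|---|---|---|---|
| Proportional | 5 / 10 / 15% | 1.021 / 1.043 / 1.066 | 1.013 / 1.038 / 1.056 |
| Milder | 5 / 10 / 15% | 1.007 / 1.015 / 1.024 | 1.002 / 1.015 / 1.020 |
| None | – | 1.000 | 0.997 |

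A smaller run on the same inputs gave no visible gain at 5%, and about 4% and 8% at 10% and 15%, under proportional growth. At 3.8%, the loss equals about 365 × 0.038 ≈ 14 patients in the first comparison.

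A second simulation (visit SDs 1.2/1.6/2.0, baseline SD 1.5, dementia status growing too) gave efficiency gains of 0.7%, 3.5%, 8.6% and 17% for Week 73 slopes of 0.15, 0.30, 0.45 and 0.60. The last slope implies (0.60 × 1.5)²/2² = 20% of variance from baseline alone, outside the 5-15% range.

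**5. Adding `DEMSTATUS*VISIT`** when dementia status also grows brought a further 0.5-1.6% in the main set and 0-3% in the second.

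**6. Shift of the Week 73 contrast.**

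- Equal dropout, main set: under 0.001 points.
- Constant effect, with severity-related dropout in the active arm only: 0.000.
- Growth, with 30% against 17% dropout or the reverse: 0.01-0.03, sign following the arm with more dropout.
- Growth, with severity-related dropout in one arm only: 0.02-0.06 in the main set and about 0.07 in the smaller run.
- Second simulation, true effect zero: 0.01-0.04 with a mild difference between arms in how dropout depends on baseline. With a strong difference, 0.08, 0.12 and 0.15 for slopes 0.30, 0.45 and 0.60; rejection was then 6.0%, 8.1% and 11.4%, and 4.0-4.2% with `BASE*VISIT`.

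**7. Cost if nothing grows.** `BASE*VISIT` adds 0.2-0.3% to the variance, both terms 0.4-0.6%, and all four covariate-by-visit terms 1.1%.

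**The case against.** The plan contains no contradiction. Text and code agree, the model is a complete MMRM, and randomisation is stratified by dementia status and APOE4. Nothing in the documents establishes growth. The nearest statement is in Protocol Section 3.3.2, "To ensure that the patients selected are likely to decline over the length of the study, two approaches have been included", but the first approach is a memory cutoff on another scale, the second is documented prior decline, and neither gives a slope for baseline CDR-SB. A constant effect, for example from measurement error in baseline, is possible, and then nothing is lost. All of this stands, and it is why the point is an improvement and not a defect.

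It can also be said that the by-visit models in Section 4.4.3 already give each covariate its own Week 73 coefficient. That is true, but they are sensitivity analyses using completers, extrapolation, last observation carried forward or a tipping point. None is a likelihood-based missing-at-random analysis. The subgroup models free the stratum effect only within strata. The cover is partial.

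A reader might infer that the 68% power is overstated, or add the gains above to it. The documents do not support either. The 68% is an unadjusted completer calculation with SE 0.250. In the smaller run in step 4, the shared-coefficient MMRM had an SE of 0.225-0.234 and power of about 73-76%, because it adjusts for baseline and uses dropouts' earlier visits. The 68% is therefore the power of neither model.

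**Conclusion.** The specification is as described, and a visit-specific baseline coefficient would be better at almost no cost. If the effect of baseline grows, Week 73 variance is roughly 0-2% too large under mild growth and about 1-8% under proportional growth, with baseline assumed to explain 5-15% of Week 73 variance. If it does not grow, nothing is lost.

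A reader might go further and infer that the primary estimate is biased or its type I error inflated. That needs both growth and arm-differential, severity-related dropout, and the documents are silent on each. The simulated shifts run from about 0.01 to 0.15 points, in either direction. They reflect chosen scenarios and are neither a forecast nor a bound.

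Nor is the protocol's ANCOVA (Section 6.4.1) evidence against the SAP model here: it adjusts for ApoE4 and clinical status only, with no baseline CDR-SB term. The stated power and confidence interval stand.

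**What to change.** Before treatment assignments are unblinded, add `BASE*VISIT`, and optionally `DEMSTATUS*VISIT`, to the primary CDR-SB model in SAP Section 4.4, in both the text and the SAS excerpt. The secondary endpoints may take the same form for consistency only; no gain was shown for them. `APOE4*VISIT` and `BAGE*VISIT` are not needed, since no gain was shown for them either.

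The cost is one line of text and code, no new data, two degrees of freedom per term (three visits), and the small variance cost in step 7 if nothing grows. The timing matters. In the main simulation the two models fell on opposite sides of p = 0.05 in 1.2% of trials with no covariate effect and in up to 6.4% with proportional growth, so a change after unblinding could look driven by the result.
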